- 2) **To study preliminary effectiveness of a D2C strategy versus standard of care** on *primary outcomes* of HIV care engagement, ART initiation or re-initiation, and viral suppression among not-in-care PLWH (n=160); and *secondary outcomes* of engagement or re-engagement in ancillary services (e.g., drug treatment) and quality of life using a cluster randomized trial design.
- 3) **To assess the feasibility, acceptability, and implementation-related processes and outcomes of the D2C strategy** using the Consolidated Framework for Implementation Research adapted for Complex Systems (CFIR-CS)¹⁵ and practice improvement notes, in-depth interviews with D2C implementers and participants, and quantitative D2C usage data.
 - a. Determine the cost of the D2C strategy and estimate the thresholds for the intervention to be cost-effective or cost-saving.

Ukraine is well-positioned as a site to identify how D2C strategies can be implemented in LMICs. With the support of international stakeholders such as PEPFAR and USAID, the Ukrainian Ministry of Health is actively promoting the use of a medical information system (MIS) at the HIV clinic level. The MIS contains patient-level information on HIV care appointments kept, medication prescriptions, all diagnosed co-morbidities, and clinical and laboratory test results.¹⁶ This information can be mobilized

D2C Ukraine

in a D2C strategy that tracks patients through the care continuum, uses data to make decisions about patient care and improve case management practices, attends to psychosocial factors that affect medication adherence (e.g., substance use), and coordinates the provision of non-clinical social services.¹⁷ Our project is positioned to institute and test strategies for maximizing the benefits of this system to improve the HIV cascade for PLWH with history of drug use.

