D2C is a structural intervention designed to sustainably change the HIV care providers' practices and facilitate information exchange at the facility level. To address the implementation science questions by measuring the provider-level outcomes and avoid contamination of the control condition due to unblinded allocation of intervention at the patient level, we propose a cluster-randomized trial design for this pilot study and the prospective RCT. We will select eligible HIV clinics (see "Study Sites," above) and randomly assign them 1:1 either to the intervention or the control arms. To achieve greater comparability between the arms, we will match pairs of eligible sites based on organizational context factors derived from Aim 1 data analysis, including facility size and type (e.g., NGO vs. public clinic), service delivery structure (e.g., social workers vs. nurses), and existing services for HIV-positive PWID (e.g. Steps Toward Health) and will randomize within the pairs. This will minimize the degree of between-cluster variation within the groups and increase power and precision.

Randomization will be conducted by the data manager using a computer program.

Sample size

We used methodology from Hayes et al⁸⁴ to determine the effect size that the intervention needs to demonstrate in a feasible matched-pair randomized trial. We assumed the cluster size of 75 patients (based on the optimal case manager workload) with 5 clusters per arm (potentially manageable number given the existing research infrastructure in Ukraine), coefficient of variation between clusters within matched pairs equal to 0.15 (empirically estimated based on the data from 56 clinics in the ART OPTI study, see Previous Studies), power of 80% and 0.05 significance level. Proportion of participants re-engaging into ART within 3 months after inclusion into the study was used as the key outcome. Under the assumptions, the relative difference between the study arms should be at least 22% (e.g. 50% vs 72%). The adjacent chart shows the power and sample size of a pilot trial needed to detect this difference with 0.05 significance level. To achieve 80% power, we will need to recruit 160 participants, or 80 per arm. We propose to divide the sample equally between 4 sites (2 per arm) to test the matching procedures. We do not adjust for loss-to-follow-up because for our main outcomes (ART initiation, viral suppression), loss to follow-up is equal to not achieving the outcome.

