- use Acuity Tool to assess patient-identified financial, socioeconomic, and housing profiles and provide comprehensive internal or external referrals for supplemental or long-term resources;
- develop and implement personalized treatment plans for all clients based on the acuity assessments through existing case management programs;
- ensure accurate tracking and documentation of all interactions and activities with patients using the acuity tool and Tracking Module within the MIS;
- establish, develop, and maintain professional relationships with diverse treatment and service providers, including AIDS care, primary care, substance use, mental health, and social services;
- maintain current contact information using the Contact Information Form (Annex 0) and updates it at each visit.

Additionally, Case Managers assist Interviewers to schedule follow-up interviews (see below) in conjunction with the Intervention sessions (at 6 and 12 months).

Control Condition

Clinics randomized to the standard of care arm will continue to implement their client identification processes and case management as usual. One of the most common interventions with a focus on PWID is Steps Toward Health,⁸⁵ a case management program developed and tested through the PEPFAR-funded RESPOND project.^{8,86} It is theory-driven and standardized in manuals that contain background information, logic models, client assessment worksheets, step-by-step instructions for each session, and monitoring and evaluation guidelines. This 5-session intervention includes modules on self-care, HIV transmission risk reduction, drug treatment, and ART adherence. It does not include active outreach, client tracking, or tailored treatment components. Other possible interventions include Community-based Retention Intervention, Patients' School, and others.

Provision of these interventions (the fact of enrollment) will be recorded in the MIS by Recruiter, but the actual process data will not be collected.

Data Collection

Data on **primary outcomes** will be obtained from clinical records in the MIS and absence of data will be equal to not achieving the outcome, therefore the effective sample size will be exactly 160 patients. Data from the MIS will be extracted monthly (Annex 6). The primary outcomes are defined as:

- Engagement in HIV care: at least 3 clinical visits over at least 6 months within 12 months after study enrollment.

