- ART (re-)initiation: initiating or re-initiating ART within 3 months after study enrollment.
- ART adherence: the percentage of days in possession of medication (pharmacy refill gap method)⁸⁷
- HIV Viral Suppression: having at least one VL test with <200cp/ml and none with >=200cp/ml within 12 months after study enrollment.

Data on **secondary outcomes** will be collected using the patient survey at baseline, 6 and 12 months after enrollment. The secondary outcomes will include items in the following domains:

- Substance Use: Substance use battery from the Ukrainian IBBS studies, AUDIT-C; DAST-10 scale for addiction severity.
- Trust in Physician Scale
- Substance Use & HIV Stigma Mechanism Scales
- Readiness for Drug Treatment Scale
- Mental Health: PHQ-9
- Risk behaviors: Risk Behavior Assessment (RBA), modified for the drug use patterns of PWID in Ukraine. The RBA assesses drug use and sex-related HIV risk behaviors.
- Quality of life: Short Form-12 (SF-12), a global measure of patient quality of life; HRQoL, HIV-related quality of life
- Medical co-morbidities and engagement in ancillary care: (OAT, TB, STI and Hepatitis treatment) by self-report.

- HIV Treatment Satisfaction Questionnaire
- Patient-side cost questionnaire
- Socio-demographic information, including age, housing status, sex/gender, family/marital status, income, education, employment status.

The surveys will be administered by an experienced Interviewer, hired at each site. The questionnaire will be programmed using REDCap platform installed on a UIPHP server.

Intervention implementation

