We have powered this pilot study to evaluate feasibility of a prospective cluster RCT. The RCT will be considered feasible if the difference in the proportion of patients achieving the primary outcome (engagement in HIV care) will reach 22% between the study arms. We will estimate the impact of the intervention on the HIV care continuum using mixed effects models. For all outcomes, the data will have the same structure, with observations (t) nested within participants (i) nested within sites (j) nested within matched pairs (k). The correlations among observations will be addressed by using fixed-effects indicators for matched pair and normally distributed random intercepts for sites and for participants. Our mixed-effects models will include indicators for each of the two follow-up assessments, an indicator for site group assignment, and two group-assignment-by-follow-up interaction terms. We will also include sex/gender, age, and baseline covariates that have been identified in preliminary analyses as varying significantly across sites. A logit link function will be used for the primary outcome of ART (re-)initiation (defined above), and the coefficients for the two group-assignment-by-follow-up interaction terms will provide the estimates of the subject-specific intervention effects at 6 and 12 months post-baseline. We will examine the effects of sex/gender, age, substance use severity, ART history at baseline and other covariates in the multivariable models.

We will characterize patterns of behavior that impact HIV transmission (episodes of syringe sharing and episodes of unprotected intercourse in the prior 30 days without viral suppression) and we will use the same mixed-effects approach described above but with a log link function and negative

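### The primary outcome is named differently from section to section; the 22-point difference behind n=160 was derived for 3-month ART re-engagement but is applied to 12-month care engagement, and adherence has no stated analysis

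*Combined protocol and SAP*

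**What the plan says.** Specific Aim 2 gives as primary outcomes "HIV care engagement, ART initiation or re-initiation, and viral suppression among not-in-care PLWH (n=160"), which is three outcomes.

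The Sample size section works with one: "Proportion of participants re-engaging into ART within 3 months after inclusion into the study was used as the key outcome". It derives a 22% difference (example 50% vs 72%) and 160 participants for that outcome. It then refers to two main outcomes, ART initiation and viral suppression, when explaining why dropout is not allowed for.

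Data Collection defines four primary outcomes:
- "Engagement in HIV care: at least 3 clinical visits over at least 6 months within 12 months after study enrollment"
- starting or restarting ART in the first 3 months on study
- a third that Aim 2 does not list, "ART adherence: the percentage of days in possession of medication (pharmacy refill gap method")
- viral suppression, from viral load tests within 12 months of enrolment.

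For all of them it says that "absence of data will be equal to not achieving the outcome", and concludes that the effective sample is exactly 160.

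Statistical Analysis and Feasibility Assessment first treats engagement in care as the primary outcome and calls the full trial feasible if the arms differ on it by 22%. Later in the same paragraph: "A logit link function will be used for the primary outcome of ART (re-)initiation". The procedures named for the analyses are mixed logistic, mixed ordinal logistic and mixed negative binomial. The ordinal model is used for care-continuum stage and the negative binomial for episodes of risk behaviour. No model is assigned to adherence.

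**The concern.** These statements are all current text, and they do not agree on how many primary outcomes there are or which one governs. The disagreement reaches the pilot's only stated decision rule. The threshold belongs to a 3-month treatment outcome, while the rule uses a 12-month visit-based outcome with a different definition. A difference that is detectable for one binary outcome is not automatically the right benchmark for another, because it depends on the control proportion and on the between-clinic variation of that outcome. At stake is whether the decision to run the full trial is tied to a threshold that was justified for the quantity being measured.

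Adherence raises a separate problem of specification. It is a percentage without a cut-off, so nothing defines achieving it. It has no time window. The analysis text says neither how patients without refill records are scored nor what link or distribution is used.

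**Working it through.** **1. The sections side by side**

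| Section | Outcome(s) treated as primary or key |
|---|---|
| Specific Aims, Aim 2 | engagement; ART (re-)initiation; viral suppression |
| Sample size, key outcome | ART re-engagement within 3 months |
| Sample size, main outcomes | ART initiation; viral suppression |
| Data Collection | the three in Aim 2, plus ART adherence |
| Statistical Analysis, feasibility rule | engagement |
| Statistical Analysis, model | ART (re-)initiation |

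**2. Reproducing the 22 points.** Inputs from Sample size: m = 75 per cluster, 5 clusters per arm, coefficient of variation k = 0.15, 80% power, 0.05 (taken as two-sided). A cluster formula of the cited type, with one cluster added per arm, is

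c = 1 + 7.849 × {[p0(1−p0) + p1(1−p1)]/m + k²(p0² + p1²)} / (p1−p0)²

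where 7.849 = (1.960 + 0.842)². For 50% vs 72%: 0.4516/75 = 0.00602 and 0.0225 × 0.7684 = 0.01729, which sum to 0.02331. Then 7.849 × 0.02331 / 0.0484 = 3.78, so c = 4.78, which rounds up to 5. At 71.5%, c = 4.94. So 22 points is consistent with 5 clusters per arm. The section calls the 22% relative, but 50% vs 61% would need c = 14.3. The absolute reading is the one that reproduces.

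**3. Reproducing 160.** Two proportions, two-sided 0.05, 80% power, no clustering:

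n per arm = [1.960 √(2 p̄ q̄) + 0.842 √(p0q0 + p1q1)]² / (p1−p0)²

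where p̄ is the mean of p0 and p1, and each q is one minus its p.

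- 50% vs 72%: (1.352 + 0.566)² / 0.0484 = 76 per arm. With 80 per arm, power is 82.0% (81.6% by exact enumeration).
- 50% vs 71.5%: (1.353 + 0.567)² / 0.0462 = 80 per arm, which is 160.

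So 160 reproduces for a single binary outcome, treated as if individually randomised.

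**4. Moving the threshold to engagement.** The documents give no control proportion or coefficient of variation specific to 12-month engagement. Keeping m, k and 5 clusters per arm, and assuming a range of control proportions, solving c = 5 for p1 gives:

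| Assumed control proportion | Smallest detectable p1 | Difference |
|---|---|---|
| 30% | 45.9% | 15.9 points |
| 50% | 71.3% | 21.3 points |
| 70% | 96.3% | 26.3 points |

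Check at 30%: (0.210 + 0.248)/75 = 0.00611 and 0.0225 × (0.090 + 0.211) = 0.00677. Then 7.849 × 0.01288 / 0.0253 = 4.0, and adding 1 gives 5. A fixed 22 points is therefore too strict or too lenient for engagement unless its control proportion is near 50%. A different k would move the figures again.

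**5. Adherence.** The other three outcomes in Data Collection are yes/no with a stated window, so absent data can be scored as failure and a logit applied. Adherence has neither. A zero-coverage rule, a cut-off, or a model for days covered would each close the gap, but the plan states none of them.

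**The case against.** This is a pilot that aims at preliminary effectiveness and at the parameters for a later trial, so loose labelling matters less than it would in a confirmatory study. That stands, and it limits how far the point may be pushed. Four stronger readings are tempting and are not supported.

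- **Inflated false-positive risk.** A reader might compute 1 − 0.95³ = 14% or 1 − 0.95⁴ = 19%. These assume independent tests, each at 0.05. The plan gives 0.05 only in the sample size calculation and sets no per-outcome level for the analysis. The outcomes are steps on one care cascade, so independence is implausible. The figures are illustrations at most.
- **Success on whichever of four outcomes is favourable.** The only stated decision rule rests on engagement alone. The fault is that its threshold came from another outcome.
- **Adherence cannot follow the failure rule, so 160 fails.** Counting days without a dispensing record as uncovered would give every patient a value. The procedure list says what the analyses will include and need not be exhaustive, and the method's details sit in a cited source that is not available here. What stands is that the plan leaves the matter unspecified.
- **ART (re-)initiation must be the sole primary outcome.** It matches the sample size, but consent follows the return visit and its routine clinical procedures, and the tracking list holds patients who had already started ART. Re-initiation may therefore often fall at or near enrolment. That is an inference, but it is reason enough to leave the choice to the sponsor.

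**Conclusion.** The point holds as a contradiction in the current text. The labels give sets of two, three and four outcomes, and two different single outcomes. The consequence that matters is the mismatch between the basis of the 22% and 160 (ART re-engagement, 3 months) and the feasibility rule (engagement, 12 months). Under the plan's own cluster inputs, the benchmark for engagement would run from about 16 to 26 points for control proportions of 30% to 70%. That range is an assumption, as is carrying k = 0.15 over to engagement. The plan's 160 itself reproduces for one binary outcome, so the arithmetic is not the fault. For adherence the finding is incomplete specification: no threshold, window, missing-data scoring or model. The finding rests on the wording of the sections and does not depend on any multiplicity argument.

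**What to change.** Name one primary outcome and use it identically in Specific Aims, Sample size, Data Collection, and Statistical Analysis and Feasibility Assessment, including the feasibility sentence. There are two coherent routes:

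- **ART (re-)initiation within 3 months.** The sample size text keeps its outcome, and the feasibility rule moves to it.
- **Engagement over 12 months.** The feasibility rule stays. The 22% and the power basis are restated for engagement, with its own expected control proportion and between-clinic variation.

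List the remaining binary outcomes as key secondary.

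Move adherence to the secondary outcomes, which also restores agreement with Aim 2. Define it as the proportion of days covered from enrolment to 12 months. Count days without a dispensing record as uncovered, so that all 160 patients have a value, and compare arms by a pair-adjusted difference in means.

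The cost is wording in the protocol and analysis plan. Primary outcome data already come from monthly extracts of clinical records, so no new visits or patients are needed for these changes. The engagement route also needs a fresh sample size justification, which may not return 160. The downside of either route is that fewer outcomes carry the primary label.

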International and Ukrainian institutions have made significant commitments to increasing the quality of HIV/AIDS services, strengthening the capacity of Ukrainian institutions to improve the continuum of HIV services for key populations, and improving access to MAT. USAID and PEPFAR both currently support efforts to improve HIV case finding, primarily through increased HIV testing and initial linkage to care. Moreover, Ukraine has expanded availability of and access to MAT, a critical component of successful retention and care for PWID.^{20-23,44-48} Our proposed D2C strategy complements these efforts and leverages the expansion of MAT in Ukraine by identifying out-of-care HIV-positive PWID and linking them with HIV and other services, including MAT. The D2C intervention would be a valuable amendment that would increase the cost-benefit ratio of any case-management intervention by timely identifying patients who need it most.

A planning grant (R34) is the ideal mechanism for this developmental project. It will allow the research team to establish the feasibility of a D2C for PWID in Ukraine and develop the tools, protocols, and management structure for implementing a full-scale trial. It will also produce important planning information on the cost of implementing a D2C in Ukraine and allow us to determine under what conditions a D2C may be a reasonable investment in Ukraine. Finally, the proposed analytic strategy will inform sample size estimation for a larger trial and determine whether ordinal logistic regression, and more specifically mixed proportional odds models, may be suitable for modeling movement along the HIV care continuum among PWID.

The **scientific premise** of this project is strong. Only 29% of HIV-infected PWID in Ukraine are virally suppressed; of PWID who are on ART, only about 74% are undetectable.⁴⁹ Connecting PLWH who are diagnosed to comprehensive case management and ancillary services can improve outcomes along the HIV care continuum. Clinical and service provision data, including viral suppression, ART prescription, medical visits, and engagement in other services, can be used to improve health outcomes for HIV-positive PWID. This D2C intervention extends current efforts to improve the availability and use of data by assessing clients with standardized, validated assessments on a range

D2C Ukraine

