Finalize the d2c strategy The finalization activities will include: (1) refining data extraction protocols and developing a case management module within the MIS; (2) developing a report generation and dissemination protocol for each clinic and (3) specify clinic/implementation team structure, roles, and management plans based on findings from in-depth interviews.

Develop data extraction protocols and create case management module within MIS

The MIS is designed as an electronic medical record system, to be used by clinical providers for routine patient data management. It has centralized architecture, where all data are immediately uploaded to a national-level server. According to the feedback we received in our ART OPTI project, tracking and prioritization of out-of-care patients is one of the most requested features for the MIS. We will partner with the Public Health Center of the MoH, the government body responsible for HIV response and coordination of PEPFAR activities in Ukraine and owner of the MIS to create a module within the MIS that will: a) identify all HIV-positive PWID meeting the criteria of not-in-care [patients registered as HIV-positive who had no HIV medical visits in a calendar year]; b) provide a useful summary of all clinical information that will be needed for case managers [drug use, CD4, viral load, ART history, HIV care appointments made and kept, co-morbid diagnoses and medications, and MAT history]; and c) provide a portal for entry and export of case management data (referrals made, appointments kept, contact attempts, case management notes).

Specific Aim 2: To pilot a randomized clinical trial of a D2C strategy versus standard of care

Study Design

[figure not shown]
This pilot study is designed to test the performance characteristics and capabilities of study design, measures, procedures, recruitment criteria, and operational strategies that are under consideration for use in a prospective RCT. We will also assess feasibility of the RCT by measuring the key parameters for sample size calculation, namely the effect size and coefficient of variation.

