Intervention Overview

Clinics randomized to the intervention arm will implement the D2C strategy as described above, including Health Data Information, Active Surveillance, and Case Management with the addition of the data component. The D2C strategy will involve a 5-step process: (1) identify not-in-care PLWH using the MIS, (2) verify eligibility criteria, (3) contact patients and invite to visit the clinic, (4) determine care status and reengage into care, and (5) provide case management services and confirm engagement in care.¹²

D2C Ukraine

Steps 1 and 2 will follow the same procedure at both intervention and control sites to ensure equal conditions of study enrollment. Step 3 will be conducted using Active Outreach at the intervention sites. Steps 4 and 5 will be achieved through use of an Acuity Tool and derived Acuity Score. The Acuity Tool will be used to identify barriers to HIV care engagement, including mental health and substance abuse, and to establish referrals to other services, as described above in Overview of Data to Care Strategies.

Procedures

Patient selection and verification of inclusion criteria

A Recruiter (clinical staff authorized to access MIS at each site) will use the D2C module in the MIS to access the “Tracking Journal” which includes patients who have a confirmed HIV diagnosis, started ART, and missed their clinical appointments (medication pick-up or other). Going through the list ('New cases' or 'In progress' or 'Not tracked' sections), Recruiter reviews the MIS data (including in other modules) and identify patients who meet the following criteria:

- a) registered within the MIS as having received a positive HIV diagnosis at any time in the past
- b) missed a clinical visit (ART pick-up or other) more than 7 days ago
- c) registered with IDU as probable mode of HIV transmission, or history of IDU documented at any clinical visit
- d) not been contacted by other clinical staff after the current missed visit
- e) 18 years or older

For each patient meeting these criteria, Recruiter puts an “E” letter in the beginning of the Comment field in the Tracking Result section (before any other text in this field, separated by a space). This letter indicates that the patient is eligible for recruitment into the study and filters the Tracking Journal to display only these patients.

Patient outreach and verification of exclusion criteria

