Next, using the contact information available in the MIS and paper documentation, Recruiter attempts to contact the patients in the E-list by phone using the procedure described in the “Tracking SOP” developed by the Public Health Center. If the contact is successful, Recruiter first has to make sure that he is talking to the intended patient, without revealing that he is calling regarding HIV treatment. Once the patient (or a trustee) identity is confirmed, Recruiter asks about the reasons of the missed visit, and assesses the following exclusion criteria and takes corresponding actions:

- Patient is already re-engaged in care and visited the clinic recently
 - In this case Recruiter verifies the MIS clinical records and updates if necessary
- Patient has sufficient supply of medications (available to him for any reason)
 - Recruiter asks about the amount, and records the date of the next visit accordingly
- Patient moved to another clinic, city, country, or penitentiary institution
 - Recruiter provides information about clinics where the patient may continue treatment and initiates the formal patient transfer procedure
- Patient died
 - Recruiter initiates the de-registration procedure

In these cases, Recruiter adds a “X” letter to the Comment field (to make “EX”). All phone contact details are recorded in the MIS.

D2C Ukraine

If the contact is successful and exclusion criteria are not met, Recruiter explains why it is important to continue treatment without interruptions and informs the patient that he or she is eligible to enroll into a research study, using a standard script (Appendix 1, two versions for the study arms). Regardless of the interest in the study, Recruiter schedules patient's next visit at the earliest convenience, and records the date in the MIS. In these cases, Recruiter adds a "L" letter to the Comment field (to make "EL").

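### Baseline viral load, a likely strong predictor held in the MIS, is not pre-specified as a covariate for the viral-suppression outcome, although entry sets no viral-load condition

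*Combined protocol and SAP*

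**What the plan says.** **Outcome.** Specific Aim 2, Data Collection, lists viral suppression among the primary outcomes and defines it as "having at least one VL test with <200cp/ml and none with >=200cp/ml within 12 months after study enrollment". The data come from the MIS, and a participant with no recorded result counts as not having achieved the outcome.

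**Entry.** Under Procedures, the recruiter works from a tracking list that "includes patients who have a confirmed HIV diagnosis, started ART, and missed their clinical appointments". The inclusion criterion on care status is "missed a clinical visit (ART pick-up or other) more than 7 days ago". None of the inclusion or exclusion criteria refers to VL. The nearest is the exclusion "Patient has sufficient supply of medications (available to him for any reason").

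**Model.** Statistical Analysis and Feasibility Assessment gives all outcomes one repeated-measures structure, with "indicators for each of the two follow-up assessments, an indicator for site group assignment" and two group-by-follow-up interactions. Sex/gender and age are always included. Other baseline covariates join if preliminary analyses show that they differ significantly between sites. Substance use severity, ART history at baseline and unspecified others are to be examined in multivariable models. Baseline VL is not named.

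**Availability.** The MIS module described in Aim 1 is to summarise, among other items, "drug use, CD4, viral load, ART history".

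**The concern.** A patient whose last VL was below 200 and who is just over a week late for a pick-up is eligible, and is probably more likely to meet the outcome than one who enters unsuppressed. Entry VL is therefore likely to be among the strongest predictors of this outcome.

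The repeated-measures structure would normally take up such a difference, because its interaction terms compare change from a baseline observation. It cannot do so here: suppression is a single value over the 12 months after enrolment and has no baseline counterpart. The plan does not say how the common model applies to it.

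Imbalance is plausible. There are two clinics per arm, and under Patient outreach only the intervention sites pass hard-to-reach patients to a case manager for further contact attempts, which can change who enrols. If the arms differ in entry VL, the unadjusted contrast carries that difference as bias. If they do not, precision is still lost. The plan uses the pilot's results for sample-size estimates in the full trial, so the quality of this estimate matters.

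**Working it through.** **The plan's own figures.** There is no stated rate for viral suppression or entry VL to reproduce. The one sample-size figure, 80 per arm for 50% against 72%, concerns ART re-engagement. A two-sided 0.05 two-proportion formula at 80% power gives 76 per arm, or 85 with continuity correction; 80 per arm gives 82.0% power. The plan's chart is not shown, so its method is unknown. Nothing below depends on it.

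**Inputs.**
- Share s with a last VL below 200 at entry: not given. Assumed 30%, 50% and 74%. The upper value borrows the Background statement that "of PWID who are on ART, only about 74% are undetectable", which describes people on ART in general, not those who have missed a visit.
- Probability of meeting the outcome: assumed a = 0.85 if below 200 at entry and b = 0.35 otherwise.
- 80 patients per arm and 4 clinics of 40: Sample size section.

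**Step 1. Outcome variance explained by entry status.** The response rate is p = b + (a − b)s. The explained fraction is (a − b)² s(1 − s) / [p(1 − p)].

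| s | p | (a − b)² s(1 − s) | p(1 − p) | Explained |
|---|---|---|---|---|
| 0.30 | 0.50 | 0.0525 | 0.2500 | 21% |
| 0.50 | 0.60 | 0.0625 | 0.2400 | 26% |
| 0.74 | 0.72 | 0.0481 | 0.2016 | 24% |

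With a = 0.75 and b = 0.25, the fractions are 22%, 25% and 20%. The size of the gap a − b matters most. If it is halved to 25 points (0.70 against 0.45), they fall to about 5% to 6%.

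**Step 2. Bias from imbalance.** With no intervention effect, the shift in the arm contrast is (a − b) × (difference in s). For a 10-point difference this is 0.50 × 10 = 5 points, or 0.25 × 10 = 2.5 points with the smaller gap.

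**Step 3. Is a 10-point imbalance plausible?** From patient sampling alone, the SD of the arm difference in s is √[2s(1 − s)/80]: 7.2, 7.9 and 6.9 points for the three values of s. Now apply the plan's between-clinic coefficient of variation, 0.15, to entry suppression. This is a further assumption, since the Sample size section uses it for ART re-engagement. The SD becomes √[2s(1 − s)/80 + (0.15s)²]: 8.5, 10.9 and 13.1 points. Ten points is therefore about one SD. Any selection through the extra outreach would come on top, in an unknown direction.

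**Step 4. Would the screen across sites catch it?** Take s = 0.50 (assumed) and four sites at 45%, 45%, 55% and 55%, the two arms differing by 10 points. The noncentrality is 160 × 0.05² / 0.25 = 1.6. A 3-df chi-square test at 0.05 then has power of about 16%. At 40%, 40%, 60% and 60% the noncentrality is 160 × 0.10² / 0.25 = 6.4 and the power about 55%. The screen would usually miss the first imbalance and would often miss the second.

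**The case against.** **Baseline VL may still get into the model.** This stands in part. The screen and the open list of other covariates leave room for it, so a reader who concludes that the plan excludes baseline VL goes too far. But the screen has low power for imbalances that matter, and ART history is not VL. The ordinal care-continuum analysis includes suppression in the prior 6 months and could be scored at baseline, but it is a separate evaluation and does not produce this outcome's estimate.

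**Patients suppressed at entry are not free successes.** This stands. A reader might infer that they succeed in either arm with no effect of D2C. The documents do not support that: they need a recorded test after enrolment and no value of 200 or more at any time in the 12 months, and absent data are failure. Keeping suppression after a missed visit may itself be an effect of D2C. It follows that shrinking a 22-point effect in proportion to the share suppressed at entry is not justified. That calculation assumes no maintenance effect, and the 22 points were not set for this outcome.

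**The share suppressed at entry may be small.** This stands as uncertainty. Patients with enough medication are excluded, and a last VL below 200 may predate the treatment gap. Aim 1 also describes not-in-care as "patients registered as HIV-positive who had no HIV medical visits in a calendar year", which conflicts with the 7-day criterion and would imply a very different share. Those two passages must be reconciled.

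**The full trial should be planned on gained suppression.** A reader might draw this from the point. It does not follow. A trial with the same eligibility needs the effect in all participants. The unsuppressed subgroup could be as small as 21 per arm (80 × 0.26). A patient tested at 200 or more after enrolment can never count as gaining suppression under the present rule.

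**Conclusion.** The point holds as a gap in pre-specification. Entry has no VL condition, the outcome uses only VLs after enrolment, and a likely strong predictor held in the MIS enters the model only by chance or by later choice. Under the assumed inputs, entry status explains about 21% to 26% of patient-level outcome variance, and a 10-point arm imbalance moves the contrast by 5 points. Both figures rest on an assumed 50-point gap in success between those suppressed and not suppressed at entry; half that gap gives about 5% to 6% and 2.5 points. The true share and gap are unknown.

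The documents do not show that the suppression result would mainly reflect entry status, or that benefit would be falsely declared. If the shares are equal in the two arms, there is no bias from this source. The sample size rests on ART re-engagement and the feasibility rule on engagement in care, so neither is affected. The change is worth making because viral suppression is a listed primary outcome and the remedy costs almost nothing.

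**What to change.** 1. Extract each participant's last VL before enrolment, with its date, from the MIS. Classify it as below 200, 200 or more, or none in the prior 12 months. Clinical procedures precede consent at the first visit, so state whether a VL drawn that day counts as entry or follow-up.
2. Pre-specify this three-level status as a fixed covariate in the viral-suppression model, whatever the screen across sites shows.
3. Tabulate it by arm and by site.
4. Report suppression by entry VL status descriptively only, with a note that the rule allowing no value of 200 or more prevents a patient so tested after enrolment from counting as gaining suppression.
5. Keep the adjusted effect in all participants as the input for planning the full trial. The outcome definition need not change.

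Cost: at most two extra fields in the monthly extraction (the field list in Annex 6 was not available, so they may already be there), a sentence or two in the analysis section, and two more model parameters. No further tests or patients are needed. Adjustment deals with measured entry VL only; other differences between four clinics remain.
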